After approval by the Research Ethics Committee of the Faculty of Medical Sciences and Health of PUC-SP and filling in the terms of consent, patients were submitted to orthopedic surgery in the lower limbs, not Hospital Santa Lucinda, and eligible to participate in the study.

Inclusion criteria:

Patients submitted to surgeries for correction of fractures in a lower hell, physical state according to an American Society of Anesthesiologists10 I and II and age between 18 and 60 years.

Exclusion criteria:

(i) refusal to participate in the study;

(ii) inability to communicate due to altered consciousness or awareness of neurological or psychiatric illness;

(iii) contraindication to the use of non-neuraxial anesthesia or allergy to any of the drugs used without study;

(iv) history of alcohol or drug addiction; and

(v) history of surgery in the last 10 days.

Drawing:

Age, sex, physical status, type of surgery, duration, history of prior surgery in the lower limbs, and presence (or not) of bladder catheterization will be recorded. Patients are randomly allocated into three groups according to a given computer-generated program measure (www.random.org):

Group D. Dexamethasone 8 mg.

Group O. Ondansetron 4 mg.

Group P. Distilled water.

For each patient, a solution to be administered through a wrap opening and sealed and containing the study group for the case. The patients involved and the data collection researchers will not be aware of the allocation. The solutions are prepared by a professional not participating in the study by diluting the agent in physiological solution or distilled water until the volume of 5 ml is complete. After a pre-anesthetic evaluation, QoR40 questionnaire and entry into the operating room, all patients are monitored with cardioscopy, noninvasive blood pressure and pulse oximetry. After a venco-lysis, midazolam will be administered intravenously before the anesthesia in titrated doses until a grade 3 or 4 sedation is obtained according to the Ramsay scale11. With the patient in position sent, the puncture subarachnoid will be performed without interspace L2-L3 or L3-L4 using 26G needle tip Quincke (B. Braun Melsungen S.A). Anesthesia will be obtained with a 0.5% hyperbaric bupivacaine injection (20 to 30 seconds) (Cristália Produtos Químicos e Farmacêuticos Ltda) at a dose of 17.5 mg if the weight is> 70 kg and / or the production> 150 minutes or 15 mg if weight <70 kg, associated with morphine (0.1 mg) without preservative (Cristália Produtos Químicos e Farmacêuticos Ltda.). The hydration will be maintained with lactated Ringer's solution. In case of failure of the block, the anesthetic procedure will be repeated or the technique will be modified for general anesthesia and the case will also be excluded. Perioperative sedation is achieved by use in metered doses (up to a maximum of 10 mg) or propofol with

the infusion rate required to achieve a level equal to or greater than 4 on a scale proposed by Ramsay.

Post-Anesthesia Recovery Room (PACU):

Patients are referred to a PACU and will remain until a criterion is reached for a discharge (score on a modified Aldrete and Kroulik scale equal to 10). 12 During the stay in the series, in the data referring to the presence of pain, nausea, vomiting, pruritus, urinary retention, temperature below 360, length of stay and other complications. Patient without complaint of pain is evaluated every 15 minutes on the numerical scale of 0 to 10, in which "zero" means absence of pain and "ten" a stronger pain than you can imagine. Morphine 1 to 2 mg intravenously will be administered every 10 minutes for a score below 4 (1 mg for pain <7 and 2 mg for pain \geq 7) when it is present. Respecting the interval of 10 minutes due to the summative effect of doses followed by morphine. However, since the patient presents with neuraxial block (spinal anesthesia), algae complaints are not expected. In view of midazolam sedation and / or proportional patient and cognitive ability to response. Nausea (and / or vomiting) treated with dimenhydrate (100mg). The pruritus will be graded according to numerical scale: zero - absence of symptoms, 1 to 3 - mild symptoms, 3 to 7 moderate modifiers and 7 to 10 - severe terms. Score above 4 will indicate the need for treatment with nalbuphine (5 mg) intravenously

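### Exclusion (iii) as printed bars contraindication to non-neuraxial anesthesia, although the trial gives a spinal block; very probably a translation slip, low severity

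*Protocol*

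**What the plan says.** Protocol, Exclusion criteria, item (iii), excludes patients with "contraindication to the use of non-neuraxial anesthesia or allergy to any of the drugs used without study".

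The anesthetic procedure, in the text that follows the allocation paragraph under Drawing, plans one starting technique: "With the patient in position sent, the puncture subarachnoid will be performed", at L2-L3 or L3-L4, with hyperbaric bupivacaine and morphine. The section Post-Anesthesia Recovery Room (PACU) names its class when it explains why pain is not expected there: "since the patient presents with neuraxial block (spinal anesthesia".

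General anesthesia appears only as a rescue: "In case of failure of the block, the anesthetic procedure will be repeated or the technique will be modified for general anesthesia". The protocol then excludes the case.

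**The concern.** The exclusion list should keep out patients in whom the planned block is unsafe. As printed, (iii) names the other class of technique. A site following the words would have no listed reason to exclude a patient whose spinal block is contraindicated on grounds other than drug allergy. It would have a listed reason to exclude someone with a contraindication only to a technique that the trial does not plan to start with. At stake are a safety-related eligibility rule and the written definition of the study population. No estimate or test depends on it.

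**Working it through.** No arithmetic beyond a count applies, and the protocol states no figure to reproduce. The check asks of each eligibility rule whether it names a contraindication to the planned neuraxial block.

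| Rule | What it covers | Names a contraindication to the block? |
|---|---|---|
| Inclusion: surgery | Fracture surgery of the lower limb | No |
| Inclusion: physical status | ASA I or II | No |
| Inclusion: age | 18 to 60 years | No |
| Exclusion (i) | Refusal | No |
| Exclusion (ii) | Inability to communicate | No |
| Exclusion (iii) | Contraindication to non-neuraxial anesthesia; drug allergy | No |
| Exclusion (iv) | Alcohol or drug addiction | No |
| Exclusion (v) | Surgery in the last 10 days | No |
| Anesthetic procedure | Exclusion after block failure | No |

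The result is 0 of 3 inclusion conditions and 0 of 5 exclusions, so 0 of 8. Adding the block-failure rule gives 0 of 9. One rule of the nine, (iii), names a contraindication to an anesthetic technique at all, and it names the wrong class.

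The rules that come nearest do not close the gap:

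- **Second half of (iii).** Read as drugs used in the study, it covers allergy to the spinal drugs. Contraindications other than allergy remain uncovered.
- **Exclusion (ii).** "inability to communicate due to altered consciousness or awareness of neurological or psychiatric illness" reaches neurological illness only where it prevents communication.
- **General limits.** "physical state according to an American Society of Anesthesiologists10 I and II and age between 18 and 60 years" restricts overall physical status and age and does not mention the block.
- **Block failure.** This rule acts after the puncture, whereas a contraindication has to act before it.

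The remaining question is which reading of (iii) was meant.

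1. *Slip.* The text puts a negative where *in* or *at* is plainly meant in other places: before the hospital's name in the opening paragraph, at the end of (iii) itself, and in "the puncture subarachnoid will be performed without interspace L2-L3 or L3-L4 using 26G needle tip Quincke". Without its prefix, (iii) agrees with the whole anesthetic plan. This reading is much the more likely.
2. *Literal.* The item might be aimed at the general-anesthesia rescue. In that case it is not a wrong word, but a contraindication to the block that participants are planned to receive is still unlisted.

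The criterion needs correcting on either reading.

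**The case against.** The strongest reply is that this describes the English rendering and not the rule the investigators used. The translation is poor throughout, and the spurious negatives form a pattern. The criticism also reads one sentence in two ways: it silently corrects the end of (iii) to mean study drugs, yet takes the prefix in the first half at face value. Read charitably throughout, the gap disappears. Read literally throughout, the protocol could not be carried out at all. A clinical check also comes before the block: "After a pre-anesthetic evaluation, QoR40 questionnaire and entry into the operating room, all patients are monitored".

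Much of this stands. A translation slip is the probable cause, literal application is not shown, and the pre-anesthetic evaluation makes harm less likely. The counts locate the gap and do not measure its consequence.

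Two things remain. The other slips are visibly nonsense, so a reader has to correct them. *Non-neuraxial anesthesia* is a coherent clinical term with the opposite meaning, so a reader can accept it as it stands. And the content of the pre-anesthetic evaluation is not stated, nor is it made an eligibility rule, so it does not supply the missing exclusion.

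**Conclusion.** The point holds as a low-severity wording error. Exclusion (iii) contradicts the anesthetic plan, and no other rule excludes a non-allergic contraindication to the planned block. Confidence is high for that comparison of wording. It does not extend to any effect on the patients enrolled: how many would be affected cannot be derived from the protocol, and nothing in it shows that anyone with a contraindication was meant to be included. The conclusion rests on the printed text being the current wording of the criterion. The consequence described arises only if that text is followed literally.

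**What to change.** Reword (iii) to exclude *contraindication to neuraxial anesthesia, or allergy to any drug used in the study*. If patients who could not receive the general-anesthesia rescue are also to be excluded, say so in a separate item, so that the two reasons are not confused.

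The cost is one wording correction in one criterion. Sample size, randomisation, endpoints and analysis do not change.

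### Does the protocol leave the three arms without a postoperative QoR-40 to compare?

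*Protocol*

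**What the plan says.** After the Drawing section, the protocol describes the sequence before anaesthesia: "After a pre-anesthetic evaluation, QoR40 questionnaire and entry into the operating room, all patients are monitored". This is the only mention of the QoR-40, and it comes before sedation and spinal puncture.

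The section Post-Anesthesia Recovery Room (PACU) gives the postoperative record. Patients "will remain until a criterion is reached for a discharge (score on a modified Aldrete and Kroulik scale equal to 10". The data belong to that stay: "During the stay in the series, in the data referring to the presence of pain, nausea, vomiting, pruritus, urinary retention", and the list continues with "urinary retention, temperature below 360, length of stay and other complications". Pain is "evaluated every 15 minutes on the numerical scale of 0 to 10", and the scores are tied to giving intravenous morphine. The same section adds that "since the patient presents with neuraxial block (spinal anesthesia), algae complaints are not expected", where the odd word is evidently a mistranslation of pain.

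On masking, the protocol says: "The patients involved and the data collection researchers will not be aware of the allocation". It does not say when the study solution is given ("For each patient, a solution to be administered through a wrap opening and sealed"), but the QoR-40 point does not depend on that.

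**The concern.** The QoR-40 measures quality of recovery. A score taken before anaesthesia and surgery cannot measure recovery from them and can serve only as a baseline. If the schedule on the page were the whole schedule, the arms could be compared neither on postoperative QoR-40 nor on change from baseline, and no later analysis plan could make up for a questionnaire that was never given.

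The rest of the postoperative record seems to share the limit. Nausea, vomiting and pruritus are recorded only up to recovery-room discharge. Pain is scored in a period when the protocol itself expects little, because the block is still acting. A trial of two antiemetic-type agents against distilled water would then say nothing about later symptoms.

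The timing of a questionnaire is normally protocol content, so it cannot be set aside as something that belongs in the statistical analysis plan.

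**Working it through.** No calculation applies. The document gives no effect size, standard deviation, event rate, alpha or sample size, so the check is a reading of each assessment against its stated time.

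| Assessment | When, in the text | Stated role |
|---|---|---|
| QoR-40 | Once, before operating-room entry | None stated |
| Aldrete-type score | Recovery room, up to discharge | Discharge criterion |
| Pain, 0 to 10 scale | Every 15 minutes in the recovery room | Guides morphine |
| Nausea, vomiting, pruritus, retention, temperature, length of stay, other complications | Recovery-room stay | Recorded data |
| Any contact after recovery-room discharge | Not described | Not described |

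**1. Count.** QoR-40 administrations: 1 before surgery, 0 after. Contacts after recovery-room discharge: 0. The literal reading is confirmed.

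**2. Is the text complete?** Three signs suggest that it is not.
- The first reference number is 10, under Inclusion criteria. Numbers 11 and 12 follow, on the sedation and discharge scales, and 1 to 9 never appear.
- There is no objective, endpoint or sample size.
- The last sentence has no full stop and falls within the recovery-room section.

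The order is preoperative, theatre, recovery room, then nothing. Ward follow-up is what would come next, so the absence coincides with the point where the text stops.

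**3. Does anything shown conflict?** A baseline QoR-40 before surgery conflicts with nothing. No sentence says that the arms are to be compared on QoR-40. If it is not an outcome, a single score defeats no stated aim. If it is, the baseline makes a planned repeat more likely.

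**4. Pain.** The scores are linked to morphine, and pain is not named as an outcome. Monitoring pain to guide treatment is compatible with expecting little of it, so the two statements do not contradict each other.

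**5. What is actually absent?** Only a postoperative QoR-40. It would be wrong to say that no recovery score exists after surgery, since discharge depends on one. That score does not fill the gap, however: discharge requires the same value of 10, and it is not among the listed data.

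**The case for a change.** The strongest case for acting is that the protocol does fix something: it puts the QoR-40 at one preoperative moment and all listed postoperative data in one short window. No gap or redaction mark appears in the recovery-room section, and the pages known to have been removed are title, signature, contact and consent pages, not a follow-up section. A repeat questionnaire by the data collectors who are already masked would need no extra patients, whereas a score never collected is lost for good.

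Part of this stands. If there is no further text and no further contact, the QoR-40 is a baseline only, and the arms cannot be compared on it. A reader should not assume otherwise.

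But the argument needs the absence to be real, and the document does not show that. It shows a sound baseline and a text that stops early. The low cost of the remedy points the same way: if the time point is already planned, the whole remedy is one sentence stating it. That is a request for clarification, not the correction of an error. The pain argument adds little, because it relies on the same missing continuation and on treating a treatment-guiding score as an outcome.

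**Conclusion.** No change follows. The observation is accurate for the text available: one QoR-40 before surgery, none after, and no contact after recovery-room discharge. The inference that recovery will not be measured is not established. The unstated time of a repeat QoR-40 is a gap that the investigators would fill as a matter of course, since a baseline on a recovery questionnaire has little use without a later score.

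This rests on two assumptions. The first is that the text is an excerpt, which the reference numbering, the missing objective and the unfinished ending support but do not prove. The second is that a baseline questionnaire implies a repeat. If both fail, the loss is the whole QoR-40 comparison together with any symptom comparison after recovery-room discharge. Its effect on an estimate cannot be sized from this document. Comparisons of symptoms and length of stay within the recovery room hold either way.

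### Does the bupivacaine dosing sentence, which overlaps below 70 kg and is silent at exactly 70 kg, need to change for the trial's comparison to stand?

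*Protocol*

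**What the plan says.** The anaesthesia paragraph that follows the list of groups under Drawing gives the dose of hyperbaric bupivacaine for the subarachnoid block. It is a "dose of 17.5 mg if the weight is> 70 kg and / or the production> 150 minutes or 15 mg if weight <70 kg". Intrathecal morphine 0.1 mg is added in every case. The paragraph applies to all patients and does not mention study group.

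The word *production* carries a unit of minutes. The list of recorded variables under Drawing includes the length of the procedure ("Age, sex, physical status, type of surgery, duration, history of prior surgery in the lower limbs"), so *production* is read here as a mistranslation of duration.

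Eligibility is set by the type of operation and by "physical state according to an American Society of Anesthesiologists10 I and II and age between 18 and 60 years", together with five exclusions. None of these limits weight or expected duration, so a patient of any weight and any length of surgery can meet the dosing rule. No other part of the protocol states a precedence between the branches or assigns the weight of exactly 70 kg.

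**The concern.** A dosing rule should send each patient to one dose, and this one does not do so on its face. The lower-weight branch has no time condition, so a light patient with a long operation satisfies both branches. Both weight inequalities are strict, so a patient of exactly 70 kg with a shorter operation satisfies neither. In those cases the anaesthetist has to choose.

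The possible harm is avoidable variation in background anaesthesia. The block matters to what is observed later: the recovery-room section says that pain is not expected while the block is working. The list of recorded variables under Drawing names neither weight nor bupivacaine dose, so on the text shown the choice could not obviously be checked afterwards. If the choice were related to study group, the comparison of dexamethasone, ondansetron and distilled water could be affected.

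**Working it through.** There is no stated sample size, power or error rate to reproduce here. The check is a truth table of the rule, followed by a test of which reading makes sense of the sentence.

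**Inputs**, all from the anaesthesia paragraph:
- Branch A: "at a dose of 17.5 mg if the weight is> 70 kg and / or the production> 150 minutes".
- Branch B: "or 15 mg if weight <70 kg".

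**Truth table**

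| Weight | Time | *and/or* read as inclusive or | Read as *and* only |
|---|---|---|---|
| below 70 kg | up to 150 min | B | B |
| below 70 kg | over 150 min | A and B | B |
| exactly 70 kg | up to 150 min | none | none |
| exactly 70 kg | over 150 min | A | none |
| above 70 kg | up to 150 min | A | none |
| above 70 kg | over 150 min | A | A |

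The inclusive reading leaves one overlap and one gap. The *and*-only reading removes the overlap but leaves everyone above 70 kg with a shorter operation, and everyone at exactly 70 kg, without a dose. It makes the rule much less complete and is hard to accept as the intended meaning.

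**Does the sentence settle the overlap?** Take the inclusive reading and ask what the time condition does under each possible precedence.
- If B governs when both apply, patients below 70 kg are always in B. Patients above 70 kg are in A by weight alone. The time condition then changes the result only at exactly 70 kg.
- If A governs when both apply, the time condition moves every patient below 70 kg with more than 150 minutes from B to A. It also places those at exactly 70 kg with more than 150 minutes in A.

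Only the second precedence gives the time condition real work. It is therefore the natural reading of the sentence, although it is not written. This is a point about grammar, not a judgement on which dose is clinically right.

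**What is left.** With that precedence, five of the six rows give one branch. The remaining row is exactly 70 kg with 150 minutes or less. Counting rows overstates the problem, since two of the six rows are the single point of 70 kg.

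**How many patients?** The protocol cannot answer this. For illustration only, assume normally distributed weight with mean 68 to 76 kg and SD 12 to 15 kg, and 10% to 30% of procedures over 150 minutes, independent of weight.
- Gap = P(recorded weight is 70) × (1 − P(long)). With whole-kilogram recording, mean 76, SD 15 and 30% long give 0.02455 × 0.70 = 0.0172. Mean 68, SD 12 and 10% long give 0.03279 × 0.90 = 0.0295. With recording to 0.1 kg the range is ten times smaller, about 0.0017 to 0.0030.
- Overlap = P(recorded weight below 70) × P(long). In whole kilograms this runs from 0.294 × 0.10 = 0.029 to 0.550 × 0.30 = 0.165.

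These ranges rest wholly on the assumed inputs, and the conclusion does not use them.

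**Effect on the comparison.** Write p for the probability that a patient falls in an unclear row. Weight and expected duration are fixed before treatment and allocation is random, so p has the same expected value in all three groups. The rule takes no input from study group. The expected difference between groups in p is therefore p − p = 0, whatever p is. The two named doses differ by 17.5 − 15 = 2.5 mg.

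**The case for a change.** The best case for asking for a change is that the gap at exactly 70 kg survives both readings, the precedence is nowhere written, and a dosing rule belongs in the protocol rather than in an analysis plan. One sentence would repair it at almost no cost. The operators and thresholds are legible, so the poor translation does not explain the defect away.

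Most of this stands as description. The gap is real, the precedence is only implied, and a later analysis plan would not be expected to supply a dose. It is also true that weight and spinal dose are absent from the list of recorded variables, although that list need not be exhaustive.

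What does not stand is the step from an untidy sentence to a consequence for the trial. The choice in an unclear case lies between two doses that the protocol itself names. Nothing in the document links that choice to study group, to any outcome or to any stated figure. One caution applies: the protocol says that patients and data collectors are unaware of allocation but does not say so expressly for the anaesthetist. The study solutions are, however, prepared to a common 5 ml volume by a professional outside the study, and the dosing rule turns on weight and time alone. The wording of the rule gives no route to differential dosing that a tidier sentence would close.

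**Conclusion.** The literal reading is correct, but the concern does not call for a change to the plan. The overlap is an unstated precedence that the sentence structure implies. The gap is a missing equals sign at exactly 70 kg with 150 minutes or less. Both lie in background anaesthesia common to all three groups, and an anaesthetist can be expected to handle them sensibly within the two doses named.

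The expected effect on the comparison between groups is nil. That rests on three things: random allocation, a rule that does not refer to study group, and the assumption that whoever chooses the spinal dose has no knowledge of allocation or no reason to act on it. The number of patients concerned cannot be derived from the protocol, and the illustrative percentages should carry no weight.

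The two branches are for the sponsor's clinical team to reconcile as a matter of wording. No view is given on doses, cut-offs or precedence, and the design and conclusions of the trial do not turn on the answer.

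### As worded, the PACU morphine rule treats only pain scores 1 to 3, so its own 2 mg dose can never be given and scores 4 to 10 get no rescue

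*Protocol*

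**What the plan says.** The rule stands in the Protocol under Post-Anesthesia Recovery Room (PACU). Pain is rated from 0 (none) to 10 (worst imaginable). Intravenous morphine, 1 to 2 mg, "will be administered every 10 minutes for a score below 4 (1 mg for pain <7 and 2 mg for pain" is 7 or higher. The dosing clause ends "2 mg for pain \geq 7) when it is present", so pain has to be present.

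Three other statements bear on the point:

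- The pruritus rule in the same section also uses a 0 to 10 scale and runs in the usual direction: "Score above 4 will indicate the need for treatment with nalbuphine (5 mg) intravenously".
- The section does not expect much pain: "since the patient presents with neuraxial block (spinal anesthesia), algae complaints are not expected".
- On blinding, the text that follows the Drawing heading says: "The patients involved and the data collection researchers will not be aware of the allocation".

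No other sentence gives a pain threshold for rescue, or any analgesic for scores of 4 or more.

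**The concern.** The sentence sets a ceiling on the scores that trigger morphine and then prescribes a dose for scores above that ceiling. Followed literally, it gives an intravenous opioid for mild pain and nothing for moderate or severe pain.

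Patient safety is the main issue. These patients have already had 0.1 mg of intrathecal morphine and midazolam, and the section itself warns about cumulative dosing when it sets the 10-minute interval. An unclear opioid trigger is a poor fit with that caution.

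The second issue is consistency. If some staff follow the words and others follow what they take to be the intention, patients with the same score will get different rescue. Morphine can change the pain, nausea, vomiting and pruritus that are recorded in the PACU.

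**Working it through.** No sample size, power or error rate is involved, and the plan has no figure to reproduce. The check lists every integer score under each reading.

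**Inputs, all from the PACU section:** scale 0 to 10; trigger, score below 4 with pain present; 1 mg if pain is below 7; 2 mg if pain is 7 or more; pruritus comparator, treat above 4.

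**Rules compared**

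- Literal: dose if 0 < score < 4.
- Correction A: dose if score ≥ 4. Titrating until the score is below 4 gives the same doses.
- Correction B: dose if score > 4, by analogy with pruritus.

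| Score | Literal | A | B |
|---|---|---|---|
| 0 | none | none | none |
| 1, 2, 3 | 1 mg | none | none |
| 4 | none | 1 mg | none |
| 5, 6 | none | 1 mg | 1 mg |
| 7, 8, 9, 10 | none | 2 mg | 2 mg |

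**Results**

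- The literal trigger is {1, 2, 3}. Ignoring the condition that pain be present adds only score 0.
- 2 mg band: {7, 8, 9, 10} ∩ {1, 2, 3} is empty, so 0 of 4 scores are reachable.
- 1 mg band with pain present: {1, …, 6} ∩ {1, 2, 3} = {1, 2, 3}, so 3 of 6 scores are reachable. The cut at 7 therefore separates nothing.
- Scores with no rescue: {4, …, 10}, which is 10 − 3 = 7 of the 10 non-zero scores.
- Literal against A: they differ at 1 to 3 (treated against not) and at 4 to 10 (not treated against treated), so 3 + 7 = 10 of 10 non-zero scores. They agree only at 0.
- A against B: they differ at score 4 only.

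Both corrections make both dose bands usable. The literal rule does not.

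**The case against.** The strongest reply is that the sentence has a sensible reading. If the words before the threshold state a purpose, morphine is repeated every 10 minutes in order to bring the score below 4. Both doses then work, severe pain is treated and the interval makes sense. The whole document reads as a poor translation, so it is very unlikely that anyone meant to withhold morphine from severe pain. Staff who see a 2 mg dose for scores of 7 or more would probably give it. The counts above are points on a scale, not patients.

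Most of this stands. The defect is one of wording, and the sentence is no evidence of an intention to leave severe pain untreated. Harm is a possibility that the document does not show occurring.

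It does not remove the point. Elsewhere the odd wording is mostly cosmetic, whereas here it reverses the trigger for an intravenous opioid. The sentence is complete and legible, so lost text does not explain it. Nor can the intended rule be fully recovered: the target reading treats score 4, and a rule modelled on pruritus does not.

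One further caution is fair. Blinding is stated for patients and data collectors only. It is not stated for the staff who give PACU morphine, so blinding makes non-differential noise likely but does not guarantee it.

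**Conclusion.** The concern holds for the text as it stands. The trigger and the dose bands in one sentence are incompatible: the literal rule treats 3 of 10 non-zero scores, leaves 7 untreated and can never reach the 2 mg dose. It should be fixed, chiefly for patient safety and so that all patients get rescue on one rule.

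The expected effect on results is small. Pain complaints are not expected under the block, and uneven rescue would mostly add noise to the PACU symptom data, subject to the caution about staff blinding. How many patients would be affected cannot be computed, because the protocol gives no rescue rate.

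The logical contradiction rests only on the quoted sentence and on integer scoring. That a mistranslation caused it is an inference.

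**What to change.** Replace the trigger in the PACU section with: *for a score of 4 or above (1 mg for scores 4 to 6, 2 mg for scores 7 to 10), repeated no more often than every 10 minutes until the score is below 4.*

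The clinical team should confirm whether score 4 itself is treated, since the pruritus rule starts above 4. If treatment is to start above 4, the 1 mg band becomes 5 to 6 and the stopping point should be changed to match. Any PACU record form that carries the rule should use the same wording.

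The cost is one protocol sentence and, where it applies, one line on a form. No extra patients, procedures or data are needed.

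### Do the shared endpoints 3 and 7 in the pruritus severity bands call for a change to the protocol?

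*Protocol*

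**What the plan says.** The Post-Anesthesia Recovery Room (PACU) section of the protocol deals with pruritus in three places.

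- **What is recorded.** The items collected during the stay are described as "in the data referring to the presence of pain, nausea, vomiting, pruritus, urinary retention" and others. For pruritus, the recorded item is its presence.
- **How it is graded.** The scale starts with "zero - absence of symptoms" and continues "1 to 3 - mild symptoms, 3 to 7 moderate modifiers and 7 to 10 - severe terms". No rule assigns a score that falls on a shared endpoint.
- **What depends on it.** One decision is attached: "Score above 4 will indicate the need for treatment with nalbuphine (5 mg) intravenously". It is triggered by the number and not by the grade.

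On blinding, the paragraph after the allocation to groups states: "The patients involved and the data collection researchers will not be aware of the allocation".

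**The concern.** A grading scheme should put each score in exactly one category. Here the upper limit of one band is repeated as the lower limit of the next, at both 3 and 7. Two assessors who both follow the text could then give different grades to the same score, and a by-group table of mild, moderate and severe pruritus would depend on a choice that the document does not make. If that choice were made after unblinding, it would be an avoidable analyst decision.

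The slip also stands out because the pain rule in the same section does use an inequality at 7: "1 mg for pain <7 and 2 mg for pain", with the complementary sign for the higher class. This is cited for its notation only.

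**Working it through.** No sample-size or power figure bears on this point, so the check is an enumeration.

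**Inputs**, all from the PACU section: none = 0; mild = 1 to 3; moderate = 3 to 7; severe = 7 to 10, limits inclusive as written; pruritus present = score > 0; treatment trigger = score > 4. Whole-number scores are assumed. The document does not say so for pruritus, but the pain scale in the same section runs from 0 to 10.

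| Score | Grade(s) as written | Present? | Above 4? |
|---|---|---|---|
| 0 | none | no | no |
| 1, 2 | mild | yes | no |
| 3 | mild **and** moderate | yes | no |
| 4 | moderate | yes | no |
| 5, 6 | moderate | yes | yes |
| 7 | moderate **and** severe | yes | yes |
| 8, 9, 10 | severe | yes | yes |

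Nine scores have one grade, two have two, and none is left without a grade.

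**Codings that fit the text.** There are two choices at 3 and two at 7, so 2 × 2 = 4. Moderate can be {4, 5, 6}, {3, 4, 5, 6}, {4, 5, 6, 7} or {3, 4, 5, 6, 7}.

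**Effect on counts.** Let n(s) be the number of patients in a group with score s.

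- Mild: n(1) + n(2), or that plus n(3). The range is n(3).
- Severe: n(8) + n(9) + n(10), or that plus n(7). The range is n(7).
- Moderate: n(4) + n(5) + n(6), up to that plus n(3) + n(7). The range is n(3) + n(7).
- Present: n(1) + … + n(10) under all four codings. The range is 0.
- Above the trigger: n(5) + … + n(10) under all four codings. The range is 0.

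The protocol gives no distribution of scores, so the first three ranges cannot be turned into percentages. The last two are zero for any distribution.

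**Is anything stated built on the first three counts?** In the document shown, no. It names no outcome based on the grade and plans no comparison of severity between groups.

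**The case for a change.** The strongest argument for a change is that this is not an omission left to the SAP: the protocol itself sets the bands and sets them ambiguously. It does not say that the raw score is stored. If only the grade were written down, no later rule could tell whether a moderate entry had been a 3, a 5 or a 7. Correcting the line would cost almost nothing.

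The literal defect stands, and so does the point that a grade without its score could not be recoded. The rest carries less weight.

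- Disagreement between assessors requires grading at the bedside with the number discarded. The document does not describe that. The treatment threshold requires a number to be obtained, and once it is kept the grade is a derived variable with one rule for everyone.
- If grading were done at the bedside, patients and data collectors are blinded, so inconsistent handling of 3 and 7 would mostly add noise and would not favour an arm. Blinding of collectors does not cover a coding chosen later by an unblinded analyst, but that matters only if a severity table is produced.
- The contrast with the pain rule is weak support. The wording is rough throughout the section, and the pain sentence is itself hard to reconcile: it refers to scores below 4 and then splits at 7. The shared endpoints may equally be a loss in translation.
- Comparing the groups on the 0-10 score would be a different analysis, and no planned comparison of severity is shown that it would improve.

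One caution limits the case for leaving the text alone. The document shown names no endpoint of any kind, so the lack of a severity endpoint says only that no use of the grade is visible.

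**Conclusion.** The bands overlap at 3 and 7, and the ambiguity covers 2 of 11 whole-number scores. It is a clerical slip with no effect on any recorded item, stated outcome or treatment decision in the protocol: presence of pruritus and the threshold of 4 come out the same under all four codings. The only thing that could move is a mild/moderate/severe tabulation, by at most n(3) in mild, n(7) in severe and n(3) + n(7) in moderate, and no such table is planned in the text shown. An analyst who wanted one would fix a single coding before unblinding and derive the grade from the score for all patients, which is ordinary practice and needs no change to the plan.

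This rests on three assumptions: scores are whole numbers, the numerical score is kept, and no outcome outside the document shown is built on the grade. If the grade did prove to be an outcome and only the grade had been recorded, the point would carry more weight.
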